3.0 Participant population

3.1 Number of Participants

Participants will be recruited from AHS and partnering affiliated health services. It is anticipated that approximately 600 participants will be screened for HCV infection using point-of-care testing, assuming that 50% of screened participants are AHS clients (HCV RNA prevalence 5%, n=15; at risk 5%, n=15) and 50% are clients of affiliated drug treatment and harm reduction services (HCV RNA prevalence 35%, n=105; at risk 65%, n=195). Enrolment will continue until at least 286 people with HCV infection (HCV RNA positive) or at risk of HCV (re)infection (HCV RNA negative) are enrolled.

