4.1 Summary of study design

Figure 1. SCALE-C study schema

This study will be conducted as an interventional cohort study. A total of 286 people with or at risk of HCV infection will be enrolled from AHS and partnering health services. Individuals at risk of HCV infection are defined by self-reported injecting drug use, incarceration or receipt of opioid substitution therapy within 12 months of screening.

Participants will receive a community-based "test and treat" intervention integrating point-of-care HCV testing, non-invasive liver fibrosis assessment (Fibroscan or APRI) and linkage to care as a strategy to increase HCV diagnosis and testing, enhance scale-up of DAA therapy and reduce HCV prevalence and incidence (Figure 1).

The "test and treat" intervention will consist of:

- Point-of-care HCV testing (anti-HCV Ab or HCV RNA)
 - Choice of initial test will be based on a short HCV risk assessment at enrolment (Figure 2)
- Non-invasive liver fibrosis assessment (Fibroscan[®] or APRI)
- Linkage to care (with medical or nursing assessment), including education regarding HCV transmission and harm reduction
- Immediate DAA initiation (if indicated and clinically appropriate)

Recruitment into the SCALE-C cohort will remain open throughout the study period. Enrolment may occur in concert with standard of care healthcare provision (following written informed consent).

To enhance recruitment and follow up targeted periods of recruitment will be developed in partnership with the participating AHS. Models of recruitment will be provided to AHS for consideration to drive recruitment. Ultimately AHS will determine appropriate models of recruitment to match their target population.

The study consists of screening, HCV treatment (8-12 weeks) if appropriate, and follow-up (up to three years post enrolment). Treated participants will transition into the HCV RNA negative at-risk cohort to assess for incident infection (reinfection) after viral cure (SVR12).

Figure 2. HCV risk assessment at screening and testing pathway

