Statistical analysis: HCV incidence will be calculated using person-time of observation. The estimated date of infection will be calculated as the midpoint between the dates of the last undetectable HCV RNA test (or end of treatment) and the first detectable HCV RNA test at the time of HCV infection. Time at risk will commence at the date of first undetectable HCV RNA (or end of treatment), and end at the estimated date of infection, death, loss-to-follow up or end of study. Confidence intervals for rates will be calculated using a Poisson distribution. Poisson regression analysis (or another time-to-event analysis) will be used to estimate crude and adjusted incidence rate ratios (IRR) and corresponding 95% CI to evaluate factors associated with incident infection.

Uptake of DAA therapy among people with HCV infection attending Aboriginal Medical Services

Hypothesis: A community-based "test and treat" intervention integrating point-of-care HCV testing will lead to increased HCV treatment uptake among people attending Aboriginal Medical Services.

Outcome: Treatment uptake (proportion of individuals with HCV infection [HCV RNA positive] initiating DAA therapy)

Statistical analysis: Among people with HCV infection, the proportion of people who initiate DAA therapy will be calculated. Factors associated with DAA uptake will be assessed by logistic regression analyses. Sample Size: Given the assumed population distribution, we will enrol 120 participants with prevalent chronic HCV infection and 29 with incident HCV infection (with spontaneous clearance in 25% of incident cases). As such, 142 will be considered for DAA therapy. Assuming DAA uptake of 70% (based on LiveRLife [unpublished data]), the 95% Cl around this estimate is 62-78%. We will have 80% power to detect an odds ratio of 2.66 or greater (alpha=0.05) for a variable that is 50% prevalent (i.e. recent injecting drug use).

Response to DAA therapy among people with chronic HCV infection

Hypothesis: A community-based "test and treat" intervention integrating point-of-care HCV testing among people attending Aboriginal Medical Services will lead to HCV treatment response of >90%.

Outcome: Treatment response (SVR, defined as HCV RNA below the lower limit of quantitation 12 weeks following end of treatment).

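### The 80% power stated for an odds ratio of 2.66 in the DAA-uptake analysis does not follow from the 70% overall uptake in the same paragraph; power is about 72-76%

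*Protocol*

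**What the plan says.** The statement is in the protocol, Section 10 (Statistics), under uptake of DAA therapy, in the sample-size paragraph.

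- **Number analysed.** "we will enrol 120 participants with prevalent chronic HCV infection and 29 with incident HCV infection"; a quarter of the incident cases are assumed to clear spontaneously, leaving 142 to be considered for treatment.
- **Outcome rate.** "Assuming DAA uptake of 70% (based on LiveRLife [unpublished data" is the assumption, with a 95% interval of 62-78%.
- **Power.** "We will have 80% power to detect an odds ratio of 2.66 or greater (alpha=0.05) for a variable that is 50% prevalent"; the example given is recent injecting.

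The paragraph does not give the uptake in the reference group, the direction of the effect, whether the test is one- or two-sided, or the formula. The planned analysis is logistic regression.

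The 120 prevalent infections come from Section 3.1. About 600 people are screened, half of them clients of Aboriginal health services (15 infected, 15 at risk) and half clients of affiliated services ("HCV RNA prevalence 35%, n=105; at risk 65%, n=195"). Section 4.1 gives the cohort size: "A total of 286 people with or at risk of HCV infection will be enrolled from AHS and partnering health services". Section 3.1 treats 286 as a minimum, and the prevalence calculation in Section 10 uses 370.

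**The concern.** An odds ratio does not fix power for a binary outcome; the outcome rate must be fixed as well. The paragraph supplies one (70%) and uses it for the confidence interval, but the power figure in the next sentence does not come out at that rate. The interval and the power therefore appear to rest on different uptake assumptions without saying so.

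This is the only power figure given for the uptake factor analysis, and recent injecting is its named example. A reader planning or interpreting that analysis would put the chance of missing an odds ratio of 2.66 at 20%, when on the paragraph's own inputs it is about 24-28%.

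**Working it through.** **Inputs** (all from the uptake paragraph): N = 120 + 0.75 × 29 = 141.75, so 142; 50% prevalent variable, so 71 v 71; uptake 70%; alpha 0.05. Two-sided testing is my assumption.

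**Step 1: what the 70% refers to.** 0.70 ± 1.96 × √(0.70 × 0.30 / 142) = 62.5% to 77.5%. This matches the printed 62-78%, so 70% is the uptake in all 142.

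**Step 2: group rates.** Solve (p0 + p1)/2 = 0.70 with [p1/(1−p1)] / [p0/(1−p0)] = 2.66. The result is p0 = 0.600, p1 = 0.800 (difference 0.1995 before rounding).

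**Step 3: power at 142.**
- Pooled two-proportion test: z = [0.1995 − 1.96 × √(2 × 0.7 × 0.3/71)] / √[(0.6 × 0.4 + 0.8 × 0.2)/71] = (0.1995 − 1.96 × 0.0769)/0.0751 = 0.65; power 74.2%.
- Unpooled: 0.1995/0.0751 − 1.96 = 0.70; power 75.7%.
- Hsieh logistic formula: √(142 × 0.21 × 0.25) × ln 2.66 − 1.96 = 2.67 − 1.96 = 0.71; power 76.2%.
- Wald test on the log odds ratio: 0.978/0.383 − 1.96 = 0.59; power 72.4%.
- Exact enumeration of the pooled test: 75.3%.

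None reaches 80%. A continuity correction lowers the figure to 67.8%. A one-sided test gives 83.5%, which does not match either.

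**Step 4: odds ratio detectable with 80% power at 142 and 70% overall.** Hsieh 2.79, unpooled 2.81, pooled 2.87, Wald 2.96. By the pooled formula, 2.66 would need about 164 infections.

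**Step 5: which inputs return the printed pair.** All at 71 v 71, two-sided, odds ratio 2.66 between groups:

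| Uptake in the two groups | Overall uptake | Power, pooled | Power, Wald |
|---|---|---|---|
| 50.0% v 72.7% | 61.3% | 79.9% | 78.3% |
| 70.0% v 46.7% | 58.4% | 81.0% | 79.5% |
| 60.0% v 80.0% | 70.0% | 74.2% | 72.4% |
| 70.0% v 86.1% | 78.1% | 64.4% | 62.4% |

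Solving the first row for 80% pooled power returns 2.664; the second returns 2.63. Both rows have an overall uptake below the lower limit of the paragraph's own interval.

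**Step 6: cohort size behind the 142 (secondary).** The Section 3.1 counts give 15 + 105 = 120 infected and 15 + 15 + 105 + 195 = 330 eligible for the cohort. The scenarios below keep 70% overall uptake; the scaling is my assumption.
- *286 enrolled, same mix.* Prevalent infections are 286 × 0.35 = 100 to 286 × 120/330 = 104. Incident cases are 29 × 286/330 = 25 up to the unscaled 29, of which 75% (19-22) do not clear. The total is about 119-126. Power is 64.8% (Wald, 119) to 71.1% (Hsieh, 126).
- *370 enrolled at 35%.* 129.5 + 21.75 = 151. Power is 75.0% (Wald) to 78.7% (Hsieh).

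**The case against.** The strongest defence is that the paragraph never says which group the 70% describes. If recent injecting lowers uptake from 70% to 46.7%, the odds ratio between groups is 2.66 and power is 79.5-81.0%, which brackets the printed figure. That direction is plausible for the named factor, and the Wald test, a natural choice for logistic regression, fits this reading better than the 50% one. What stands is that the source of the figure cannot be established. A reader might infer that the authors used 50% uptake in the reference group because it matches 2.66 most closely; the document does not say so, and a second set of inputs comes close. This defence does not rescue the sentence, however. It needs 58% overall uptake, outside the stated 62-78%, while the interval treats 70% as the rate in all 142. It also needs the groups recoded for the odds ratio to exceed 1, as the text has it.

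A second objection concerns enrolment. A reader might conclude that true power is 65-71%, with a miss risk of about 30% or more, because the cohort is 286. The documents do not support this as the finding. The 142 agrees with its source, about 600 screened; 286 is a minimum with recruitment kept open; and 370 appears elsewhere in Section 10. The 119-126 count is a scenario.

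Third, this is a factor analysis within a secondary endpoint, with no decision rule attached. Nothing in the protocol says that a null result would be read as excluding an odds ratio of 2.66. That is fair and limits the weight of the point.

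**Conclusion.** The point holds as an internal inconsistency in one paragraph. At the 70% overall uptake that its own interval implies, 142 infections give about 72-76% power for an odds ratio of 2.66, a shortfall of about 4-8 percentage points. Equivalently, the odds ratio detectable with 80% power is about 2.8-3.0. This assumes a two-sided 5% test, an even split on the factor and no continuity correction.

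The 120 prevalent infections match the Section 3.1 assumptions, but the paragraph does not say which cohort size it presumes. None of the sizes 286, 330 or 370 brings the power to 80% at 70% overall uptake under these assumptions. The stated precision of 62-78% at 142 is correct. The primary endpoint is not affected.

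**What to change.** Rewrite the power sentence of the uptake paragraph in Section 10 from one set of inputs. With 142 infections, 70% overall uptake, a 50% prevalent variable and two-sided alpha of 0.05, state that the odds ratio detectable with 80% power is about 2.9. Alternatively, keep 2.66 and state power of about 74-76%. Name the formula, since the Wald version gives 72%.

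If a different reference-group uptake or a factor that lowers uptake was intended, state the two group rates and reconcile them with the 70% and its interval.

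Add a clause saying that the 120 prevalent infections presume about 600 screened and 330 cohort members, or give the figures for whichever enrolment number the protocol settles on.

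The cost is a wording change and a slightly less favourable figure for a secondary analysis. No added participants or procedures are needed.

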In Australia, an estimated 300,000 people have reported injecting an illicit drug at least once, and 90,000 reported injecting drug use (IDU) in the past year (5). The majority of existing (80%) and new (90% of 9,000 cases per annum) HCV infections are among PWID (6). Available evidence suggests that the prevalence of IDU is considerably higher amongst the Aboriginal (3-8%) than the non-Aboriginal (1-2%) population, and has increased over recent years (7-10). Among Aboriginal PWID, recent HCV prevalence estimates range between 59-70% (7, 11). HCV incidence is markedly higher in Aboriginal PWID (31 per 100 py, 95% CI 19, 50) than in the general PWID population (11 per 100 py, 95% CI 9, 14) (12). Compared with non-Aboriginal PWID, Aboriginal PWID are more likely to start injecting at an early age, report receptive needle sharing, inject more frequently and in public and have a history of incarceration (7, 9, 12, 17).

Furthermore, Aboriginal people account for 27% of the Australian prisoner population, with 76% having experienced repeated episodes of incarceration (13). Among Aboriginal prisoners in 2013, prevalence of chronic HCV was 31%, with higher prevalence among prisoners who were also PWID (54%) (14). Combined, this data highlights the need to implement targeted HCV testing, care and treatment, along with culturally-appropriate harm reduction strategies, for Aboriginal people.

Improving access to HCV therapy in Australia

Oral direct-acting antiviral (DAA) treatments have revolutionised the management of HCV infection and given rise to optimism about the potential for HCV elimination in Australia. However, marginalised populations often fare less well in relation to access to health care innovations, and this is particularly the case for Aboriginal people. In this context, it cannot be guaranteed that the roll out of new HCV treatments will have equal impact for Aboriginal people. Understanding how HCV treatment is accessed by Aboriginal people is essential to avoid creating further gaps in liver disease and Aboriginal health outcomes.

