2.3 Secondary objective(s)

- To evaluate the impact of a community-based "test and treat" intervention on HCV incidence among people attending AHS;
- To evaluate DAA treatment uptake among people with HCV infection;
- To evaluate response to DAA therapy among people initiating treatment for HCV infection, and assess factors associated with failure to achieve SVR;
- To evaluate the proportion of participants who complete treatment;
- To evaluate treatment adherence among those who commence DAA therapy;
- To calculate HCV reinfection incidence, and assess factors associated with reinfection.

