9.7 HCV RNA Recurrence

Among people with an end of treatment response, participants with HCV RNA recurrence (detectable HCV RNA) will be identified. HCV sequencing will be performed from dried blood samples using Core-E2, NS5A or NS5B Sanger sequencing (23). HCV reinfection will be defined by the detection of infection with a strain distinct from the primary infecting strain based on defined genetic distance-based cut-offs and phylogenetic tree construction for reinfection and relapse developed by the investigators (23).

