9.8 Future use of biological samples

After the samples have been analysed for the study endpoints as specified in the protocol, remaining samples will be stored for use in future Human Research Ethics Committee approved hepatitis C related research. Additional consent will be sought for permission to store any remaining DBS samples after sample analyses for study endpoints for future hepatitis C related research. As part of the informed consent process and form, participants will indicate their choice using tick boxes to the storage of remaining samples for use in hepatitis C related future research. Samples from participants who indicate they do not wish for their samples to be used in future research, will be destroyed, or returned to participates if indicated, following sample analyses for study endpoints

10. Statistics

Statistical Analyses and Sample Size Calculations

Primary endpoint: The primary endpoint for the HCV treatment as prevention evaluation is HCV prevalence following implementation of the community-based "test and treat" model.

Secondary endpoints include:

- HCV incidence;
- DAA uptake: Proportion with HCV infection initiating DAA therapy;
- DAA treatment outcome: Proportion who initiated DAA therapy and achieved SVR (defined as HCV RNA below the lower limit of quantitation at post treatment week 12);
- DAA treatment completion: Proportion who completed prescribed treatment course;
- Adherence;
- Reinfection incidence post treatment.

The impact of rapid DAA treatment scale-up on HCV incidence and prevalence

Hypothesis: Rapid DAA scale-up will reduce HCV prevalence by >50%

Outcome: Prevalence of HCV infection

Statistical analysis: The proportion of people with current HCV infection (HCV RNA positive) will be calculated by study period. Confidence intervals for proportions will be calculated.

Sample Size: With enrolment of 370 participants (estimated HCV RNA prevalence in Year One, 35%; alpha=0.05; loss to follow up, 30%), the study has 90% power to detect a relative reduction in HCV RNA prevalence of 50% from the initial to the later study period following scale-up of testing and treatment.

Hypothesis: Rapid DAA scale-up will reduce HCV incidence by >50%

Outcome: Incidence of HCV infection

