Statistical analysis: The proportion of people achieving SVR12 will be calculated with corresponding 95% CI. Factors associated with treatment response will be assessed by logistic regression analyses.

The proportion completing the prescribed treatment course will be calculated with corresponding 95%CI. Factors associated with treatment completion will be assess by logistic regression analysis.

Estimate incidence of HCV reinfection after successful DAA therapy

Hypothesis: HCV reinfection following treatment will be associated with ongoing high-risk behaviours facilitating transmission.

Outcome: Incidence of HCV reinfection following DAA therapy

Statistical analysis: Rates of HCV reinfection following treatment will be calculated using person-time of observation, with the methodology described in Aim 1, except that time at risk will commence at the date of end of treatment. Poisson regression analysis (or another time-to-event analysis) will be used to estimate crude and adjusted IRRs and corresponding 95% CI to evaluate factors associated with reinfection.

11. Data Safety and Monitoring Board (DSMB)

A Data Safety Monitoring Board will not be used for this study as treatment is being prescribed and supplied according to PBS indications.

12. Data collection, source documents and record retention

The Principal Investigator and the institution where the study will be conducted will permit study-related monitoring, audits, ethics committee review and regulatory inspection providing direct access to source documents.

Data will be collected on study specific electronic or paper copy case record forms. The Principal Investigator is responsible for ensuring the data collected are complete, accurate and recorded in a timely manner.

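### SVR12 is defined by RNA alone, so early reinfections join virological failures in the non-SVR group, and the protocol gives two different starts for reinfection follow-up

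*Protocol*

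**What the plan says.** Two places in Section 10 fix the response outcome. The endpoint list gives "Proportion who initiated DAA therapy and achieved SVR (defined as HCV RNA below the lower limit of quantitation at post treatment week 12", with everyone who started DAA therapy as the denominator. The response analysis repeats the rule: "Treatment response (SVR, defined as HCV RNA below the lower limit of quantitation 12 weeks following end of treatment". Neither refers to strain or sequence. The hypothesis is that the intervention "will lead to HCV treatment response of" at least 90%.

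Section 2.3 sets the objective to "assess factors associated with failure to achieve SVR", and Section 10 implements it: "Factors associated with treatment response will be assessed by logistic regression analyses".

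For recurrence among people with an end-of-treatment response, Section 9.7 states: "HCV reinfection will be defined by the detection of infection with a strain distinct from the primary infecting strain". Section 10 applies the general incidence method to reinfection, "except that time at risk will commence at the date of end of treatment". Section 4.1, however, moves treated participants into the at-risk group for reinfection only after cure at SVR12, and the Section 10 heading for this analysis refers to reinfection after successful therapy.

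Section 3.2 defines prior DAA treatment failure as on-treatment failure or post-treatment relapse, and keeps people reinfected after DAA therapy eligible for treatment. Section 9.1 says sequencing may be used to tell relapse from reinfection and to study factors associated with relapse. Nothing links that result to the SVR outcome or its regression model.

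**The concern.** There are 12 weeks between end of treatment and the visit that determines SVR. A distinct-strain infection acquired in that window gives quantifiable RNA at the visit and is recorded as non-SVR, although the original infection was cured. The non-SVR group is then a mixture of virological failures and early reinfections.

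The failure-factor model is the part most exposed. True virological failures are expected to be few, so one or two reinfections can be a material share of the modelled events. Section 10 itself hypothesises that ongoing risk behaviour predicts reinfection. With a mixed outcome, the same behaviour could appear as a predictor of not responding to the drug.

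The second issue is the start of reinfection time. Under Section 10 the early case is also a reinfection event. Under Section 4.1 it is non-SVR only and drops out of the reinfection analysis. Both the numerator and the person-time of the reinfection rate depend on which rule is followed.

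**Working it through.** **The protocol's own figures first.** Section 10 (uptake) puts 142 people forward for DAA therapy: 120 + 29 × 0.75 = 141.75, which rounds to 142. With 70% uptake, the Wald interval is 0.70 ± 1.96 × √(0.70 × 0.30 / 142) = 62.5% to 77.5%, matching the stated 62–78%. Both reproduce. The protocol gives no sample size, power or interval for SVR itself.

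**Inputs.**
- Starters: 142 × 0.70 = 99.4, taken as 99.
- Cure: 95% (Section 1.0 gives above 95%).
- Window: 12 weeks, 84 / 365.25 = 0.230 years.
- Early reinfection rate: the protocol gives none, so this is an assumption with a range:
  - 29 incident infections (Section 10) over 715 person-years (synopsis) = 4.1 per 100 py. The protocol does not itself state this as an incidence.
  - 11 per 100 py for people who inject drugs in general (Section 1.0).
  - 31 per 100 py from Section 1.0: "HCV incidence is markedly higher in Aboriginal PWID (31 per 100 py, 95% CI 19, 50".

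**Formulas.**
- P = 1 − exp(−rate × 0.230), the probability of reinfection in the window
- Observed SVR = 0.95 × (1 − P)
- Early reinfections = 99 × 0.95 × P
- Virological failures = 99 × 0.05 = 4.95
- Share = early reinfections / (early reinfections + 4.95)
- The last column is the binomial probability of at least 90 responders out of 99. It is 0.97 with no early reinfection.

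| Rate per 100 py | P | Observed SVR | Early reinfections | Share of non-SVR | P(observed SVR ≥90%) |
|---|---|---|---|---|---|
| 4.1 | 0.9% | 94.1% | 0.9 | 15% | 0.93 |
| 11 | 2.5% | 92.6% | 2.3 | 32% | 0.81 |
| 31 | 6.9% | 88.5% | 6.5 | 57% | 0.28 |

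Taking the window as 12/52 of a year gives 88.4% instead of 88.5% in the last row.

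**Break-even.** The rate that moves SVR from 95% to 90% is −ln(0.90 / 0.95) / 0.230 = 0.235, or 23.5 per 100 py.

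These figures assume that everyone attends the week-12 visit and that no early reinfection clears spontaneously before it. Allowing for clearance would make the effect somewhat smaller.

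**The case against.** The strongest reply is that RNA-only SVR12 is a legitimate outcome. The hypothesis concerns what the community-based programme achieves and the denominator is everyone who started therapy. For programme effectiveness, being free of virus at week 12 is a coherent target whatever the strain. This stands: the definition is not wrong in itself, and calling the result biased is fair only relative to drug response.

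A reader might infer that every early reinfection is counted twice. The documents do not settle that. It follows from the Section 10 start at end of treatment, but not from Section 4.1. Appearing in two endpoints that answer different questions is not in itself an error either.

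A reader might also infer that the 90% target is put out of reach. The protocol plans a proportion with a confidence interval and no test against 90%. The 11 and 31 per 100 py rates are background rates in people who inject drugs, not post-treatment rates in this mixed cohort. At the rate implied by the planning figures the shift is about one percentage point.

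Section 9.1 does foresee some relapse-specific work, and an analysis plan that is not shown could add a second SVR figure. But that sentence is permissive and tied to no endpoint, whereas the protocol does fix the RNA-only outcome and the regression on it. The conflict over the start of risk time is in the protocol text itself.

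**Conclusion.** The point holds in a limited form. As written, the non-SVR group mixes distinct-strain reinfections acquired before week 12 with virological failures. The failure-factor model inherits that mixture, although Section 3.2 describes DAA failure in terms that leave reinfection out. Sections 4.1 and 10 disagree on when reinfection follow-up begins.

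For the SVR proportion the effect is small to moderate: 0.9 percentage points at the planning rate, 2.4 at 11 per 100 py and about 6.5 at 31. It takes SVR below 90% only above about 23.5 per 100 py. For the failure-factor model it matters more, because only about 5 true failures are expected and reinfections would be 15% to 57% of modelled events. All of this rests on 95% cure, about 99 starters and the assumption that the quoted rates apply after treatment.

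The documents do not support the stronger claims that the SVR definition is invalid, that double counting is certain, or that a formal conclusion about 90% would be distorted. This is an inexpensive improvement to a secondary endpoint, together with one inconsistency that must be resolved.

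**What to change.** In Section 10:

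1. Keep RNA-only SVR12 as the defined outcome.
2. Add a second pre-specified response figure in which participants with an end-of-treatment response and sequence-confirmed distinct-strain RNA at post-treatment week 12 are not counted as virological failures. State whether they count as responders or leave the denominator, since these give different proportions.
3. Analyse factors for failure on virological failure or relapse, and count the reclassified cases as events in the reinfection analysis.
4. Reconcile Sections 4.1 and 10 so that reinfection risk time has a single start.

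The cost is wording and one extra proportion. Dried blood spots at end of treatment and week 12 are already scheduled, and sequencing of recurrences is already planned in Section 9.7.

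There are downsides. Two response figures need explaining. About 5 virological failures will support little beyond description, so the regression would be weak. Recurrences that cannot be sequenced would stay as failures. A mixed infection at baseline, which Section 9.1 recognises as possible, could be misread as a new strain and raise the second figure, so reporting both figures side by side is important.
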